Study treatment	Any drug or combination of drugs or intervention administered to the study participants as part of the required study procedures; includes investigational drug(s), control(s) or background therapy.

Treatment arm/group	A treatment arm/group defines the dose and regimen or the combination, and may consist of 1 or more cohorts.
Treatment of interest	The treatment of interest and, as appropriate, the alternative treatment to which comparison will be made. These might be individual interventions, combinations of interventions administered concurrently, e.g. as add-on to standard of care, or might consist of an overall regimen involving a complex sequence of interventions. This is the treatment of interest used in describing the related clinical question of interest, which might or might not be the same as the study treatment.
Variable (or endpoint)	The variable (or endpoint) to be obtained for each participant that is required to address the clinical question. The specification of the variable might include whether the participant experiences an intercurrent event.
Withdrawal of study consent (WoC)/	Withdrawal of consent from the study occurs when the participant explicitly requests to stop use of their data and biological samples
Opposition to use of data /biological samples	(opposition to use data and biological samples) AND no longer wishes to receive study treatment, AND does not want agree to further protocol required assessments. This request should be in writing (depending on local regulations) and recorded in the source documentation.
	Opposition to use data/biological samples occurs in the countries where collection and processing of personal data is justified by a different legal reason than consent.

Page 13 of 98

Protocol Amendment 01 (20-Dec-2021)

Amendment Rationale

Novartis

As of the date of release of this protocol amendment, 20 subjects have been randomized in the study (12 dosed).

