The main purpose of the amendment is to clarify the inclusion criterion on PSA level requirements for confirmation of biochemical recurrence (BCR) following radiation therapy and following Radical Prostatectomy (RP) to avoid misinterpretation and ensure full alignment with the published definitions for BCR per AUA and ASTRO-Phoenix guidelines and with the targeted study population (patients who have BCR following initial definitive therapy). The amendment also clarifies that subjects with prior salvage radiation therapy or salvage surgery are not eligible for the study to ensure alignment with the targeted patient population. Other clarifications and corrections of discrepancies or errors have been implemented across the protocol. All changes implemented are detailed below with their justification.

The changes described in this amended protocol require IRB/IEC approval prior to implementation.

A copy of this amended protocol will be sent to the Institutional Review Board (IRBs)/Independent Ethics Committee (IECs) and Health Authorities.

The changes herein do not affect the Informed Consent.

Main changes implemented in the protocol amendment				
Section	Change	Description and rationale		
Protocol summary Section 2.1 Section 3 Section 5	Targeted population in the study Additional information provided.	Clarification that targeted population for the study is prostate cancer patients diagnosed with biochemical recurrence (BCR) after initial definitive therapy (with either RP or curative intent RT)		
Section 3	Clarification of safety assessments follow-up timing	Updated to ensure that safety assessments to be performed at the safety follow-up at 14 days (+ 3 day window) after each PET/CT scan day are also performed before any surgery/radiation therapy/initiation of antineoplastic medication, in the event where the patient would undergo surgery, radiation therapy or initiating any antineoplastic medication (provided all CTS procedures have been completed before this initiation) prior to planned safety visit.		
Protocol summary Section 5.1	Update of Inclusion criterion #3 For patients who had prior RP, BCR must be confirmed by an initial serum PSA of ≥0.2 ng/mL measured at least	Modified inclusion criterion (numbered 3a) to clarify the requirements for biochemical recurrence (BCR) following initial definitive therapy with either RP or curative-intent radiation therapy (RT) and fully align with the definitions of BCR from the publications referred to for AUA		

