Section 3	Clarification on Standard of Care	Clarification that the high resolution CT
Section 4.1	imaging part of CTS	scan and any other imaging diagnostic procedure clinically indicated as per SoC
Section 8.3.1	level 2 timing	part of CTS level 2 must be acquired
	10 / 01 = vg	within the 8 weeks either prior to or
		following the [18F]CTT1057 PET/CT scan.
Section 8.3.1	Addition of Table 8-2	Addition to provide clarity to sites on the
		imaging procedures expected for this study
		and their timing. Subsequent tables in the
		document were re-numbered accordingly.
Section 8.3.1		
Section 8.3.1	Clarification on	Clarification that the characteristics of
Section 6.3.1	Characteristics of	lesions should be documented for lesions
	lesions	that are visually positive on the [68Ga]Ga-
		PSMA-11 PET but not considered as
		prostate cancer (i.e. non prostate cancer
		tumoral lesions, or benign non tumoral
		lesions).
Section 3	Addition of a new	Addition of a new option named
Section 12.5.1	option in questionnaire	"Radiation alone with change in radiation
Section 16.4	#2	treatment plan", which will be applicable
(Appendix 4)		only for questionnaire 2, in order to capture any intended change in the radiation plan
		any michaed change in the fadiation plan

		(e.g. change in the extent of the field of radiations).
Section 6.2.1	Clarification of use of diuretics	Clarification that the use of diuretics (e.g. furosemide) to help subject to void before PET/CT scan imaging acquisition is allowed in case of need, upon the discretion of the investigator.
Section 6.2.2	Clarification of use of LHRH analogues and anti- androgens	Clarification that use of any ADT including LHRH analogues (agonists or antagonists) as well as anti-androgens (both first and second generation compounds) and 5-alpha reductase inhibitors is prohibited prior to completing both PET imaging scans and CTS procedures, to ensure that the same lesions are assessed on PET/CT scans and CTS procedures without potential reduction in lesion size and therefore detectability due to administration of antineoplastic medications.
Section 8.5.1	Clarification of patient management questionnaire #2 Timing for completion	Clarification that patient management questionnaire 2 should be completed before [⁶⁸ Ga]Ga-PSMA-11 PET/CT is performed for subjects assigned to sequence 1.

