## **Document History – Changes compared to previous final version of SAP**

Date	Time point	Reason for update	Outcome for update	Section and title impacted (Current)
10- Oct- 2021	After FPFV	Creation of final version	N/A - First version	NA
03- Oct- 2022	After PA01, before original IND submission	Incorporating changes made in the protocol amendment v01.	1. Clarification added to the targeted population, i.e. prostate cancer patients diagnosed with biochemical recurrence (BCR) after initial definitive therapy (with either RP or curative intent RT).	Section 1.1, 1.2, 2.1.1, 2.2, 2.3.1, 2.5.6, 2.6, 2.7, 2.12, 3 and Section 5.
			2. Clarification of the different CTS levels will be applied hierarchically at lesion level for efficacy analyses added.	
			3. Addition of a new option named "Radiation alone with change in radiation treatment plan" for questionnaire 2.	
			4. Clarification added that the secondary endpoint (based on central imaging reads) and	
			for concordance between [18F]CTT1057 and [68Ga]Ga-PSMA-11 for detection of PSMA-positive lesions (in terms of number of lesions detected and their location) will be assessed at lesion level, not patient level.	
			5. Updated the definition of efficacy analysis set to align with PA01.	
			6. Updated the 2 subgroups for subgroup analyses to patients with prior RP and patients with prior curative intent RT.	
			7. Modified analyses to be performed regarding patient	

Date	Time point	Reason for update	Outcome for update	Section and title impacted (Current)
			disposition output to fully align with SC meeting.	
			8. Added details regarding a supplementary analysis for the primary endpoints. 9. Removed the sentence about aggregating results among readers for the intra-reader variability calculation. 10. Added COVID-19 related AE summaries and two required tables by ClinicalTrials.gov. 11. Added 3-day time window for post-baseline lab and vital sign	
			assessments.	
			13. Minor typographical corrections, removal of duplicated wording and minor rewording implemented across the document.	

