Change in patient management plans attributed to the [18F]CTT1057 PET/CT scan is defined as the percentage of participants who undergo a change in intended treatment plan attributed to

the PET/CT scan as assessed by pre-imaging questionnaire 1 and post-imaging questionnaire 2.

The number and percentage of participants from the F-SAF for each of the following categories of treatment plan in each of the two questionnaires will be calculated: surgery, radiation alone, radiation alone with change in radiation treatment plan (only applicable for questionnaire 2), radiation plus ADT, ADT alone, observation/surveillance, other (free text box).

Treatment plan change is defined as a change in the pair of categories (one category of questionnaire 1, one category of questionnaire 2).

The number and percentage of participants from the F-SAF with treatment plan change as defined above will be calculated. Shift tables comparing treatment plans between questionnaire 1 and 2 will be displayed. The number (%) of participants with and without a change in treatment plans by [18F]CTT1057 local read results (i.e. positive, negative, and inconclusive) will be tabulated.

**Region-level sensitivity** is defined as the proportion of TP regions among those that are TP or FN

**Region-level specificity** is defined as the proportion of TN regions among those that are TN or FP

**Region-level negative predictive value** is defined as the proportion of TN regions among those that are TN or FN

**Region-level accuracy** is defined as the proportion of TP and TN regions among those that are identified on [18F]CTT1057 (regardless of TP, TN, FP, FN)

where TP, TN, FP, FN regions are defined as follows:

- PSMA TP regions are regions containing at least one TP lesion (anatomically localized correspondence between [18F]CTT1057 PET imaging and the CTS).
- PSMA TN regions are regions containing no lesions with pathological [18F]CTT1057 uptake and confirmed by CTS.
- PSMA FP regions are regions containing lesions with pathological [F]CTT1057 uptake but are verified negative by CTS or none is correctly localized in anatomical location by the CTS.
- PSMA FN regions are regions containing no lesions with pathological [F]CTT1057 uptake but are confirmed as having at least one lesion with the CTS.

Number of TP, TN, FP, FN regions will be presented and used to calculate the diagnostic performance parameters.

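### The management-change percentage pools Questionnaire 2 forms from before and after the radiation-plan option was added, so it may be slightly understated

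*SAP*

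**What the plan says.** The Protocol Amendment 01 table of main changes adds a Questionnaire 2 category for radiation alone with an altered radiation plan. It applies "only for questionnaire 2, in order to capture any intended change in the radiation" plan, with the example "e.g. change in the extent of the field of radiations". The Amendment Rationale, dated 20-Dec-2021, gives the exposure at release: "20 subjects have been randomized in the study (12 dosed". It also states: "The changes described in this amended protocol require IRB/IEC approval prior to implementation".

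The scoring rule is in SAP 2.6.1: "Treatment plan change is defined as a change in the pair of categories (one category of questionnaire 1, one category of questionnaire 2". The population follows: "The number and percentage of participants from the F-SAF with treatment plan change as defined above will be calculated". SAP 2.2 defines the F-SAF as everyone who received [18F]CTT1057, whenever they enrolled. SAP 2.6.1 also asks for counts and percentages in every category, including the new one, for shift tables, and for change by local read result.

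None of these outputs is split or restricted by form version. SAP 2.6.5 plans no sensitivity analyses for secondary endpoints. SAP section 4, on departures from the protocol's analyses, does not mention the questionnaire.

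**The concern.** The instrument for a secondary endpoint changed during enrolment, and the scoring rule depends on which categories the form offered. Take a participant planned for radiation whose field is altered after the scan. On the amended form his pair is 'Radiation alone' followed by the new option, which is a change. On the old form the natural pair is 'Radiation alone' twice, which is no change.

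Two results are affected. The overall percentage mixes two working definitions of change, and for this event the difference runs only towards no change. The percentage in the new category has a denominator that includes participants who could not have been recorded there.

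Protocol 4.1 includes this endpoint to describe clinical impact, and the sponsor thought radiation-plan changes worth a new category. The endpoint is also reported by prior therapy (SAP 2.2.1). Old forms would weigh more in those smaller denominators if they clustered in one subgroup.

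**Working it through.** The plan states no expected rate, sample size or power for this endpoint, so it has no figure of its own to reproduce. The size can only be bounded.

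**Inputs**
- N, the F-SAF size: about 190 enrolled, and at least 152 evaluable after the planned 20% loss (190 × 0.80 = 152; Protocol 12.8, SAP 3). Every evaluable participant received [18F]CTT1057, so under the plan the F-SAF lies between these values.
- m, the number of Questionnaire 2 forms completed without the new option: not stated. The reference points are 12 dosed and 20 randomised at the amendment's release.
- q, the share of those m participants whose plan stayed 'Radiation alone' in both questionnaires although the radiation plan changed: not stated, so assumed.

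**Overall percentage**

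Understatement in points, relative to using the amended form throughout, is 100 × m × q / N. The ceiling is q = 1. Each old form can contribute at most 100/190 = 0.53 points.

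| m | Basis | Ceiling (q = 1) | q = 10% | q = 25% | q = 50% |
|---|---|---|---|---|---|
| 6 | assumption: half of the 12 had received only the gallium tracer and later used the amended form | 3.2 | 0.3 | 0.8 | 1.6 |
| 12 | dosed at release | 6.3 | 0.6 | 1.6 | 3.2 |
| 20 | randomised at release | 10.5 | 1.1 | 2.6 | 5.3 |
| 30 | assumption: approval lag | 15.8 | 1.6 | 3.9 | 7.9 |

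All rows use N = 190. For example, 100 × 12/190 = 6.3 and 100 × 20 × 0.25/190 = 2.6. With N = 152 the ceilings for 12 and 20 forms become 12/152 = 7.9 and 20/152 = 13.2 points.

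For scale, the 95% half-width of a proportion near 50% with N = 190 is 1.96 × √(0.25/190) = 7.1 points.

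**New-category percentage**

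If x participants are recorded in the new category, the SAP reports x/N, while the rate among those offered it is x/(N − m). The ratio is (N − m)/N: 178/190 = 0.937 for 12 old forms and 170/190 = 0.895 for 20. The reported figure is therefore 6.3% to 10.5% too small in relative terms. This does not depend on q or on use of 'Other'.

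**The case against.** Several points on the other side stand.

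- **The number of old forms is unknown in both directions.** A reader might take 12 as a minimum. The documents do not support that. The rationale does not say which tracer the 12 had received, and Protocol 6.1 counts either agent as study treatment. Sequence 2 participants receive [68Ga]Ga-PSMA-11 first and [18F]CTT1057 at least 14 days later (Protocol section 3), and Questionnaire 2 may follow the result by up to 14 days. Some of the 12 may have completed it later, on the amended form. Conversely, the wait for ethics approval could take the number above 20, but nothing says how far.
- **Downward bias is possible, not established.** The old form is not in the documents. The change log names one added option, which suggests that the free-text 'Other' already existed. A field change entered there gives a different pair and counts as change. Early forms may also have been queried or updated.
- **The rate is unsupported.** Only participants with 'Radiation alone' on Questionnaire 1 can be missed this way, and the documents give no share for them. The ceilings require every old-form participant to be such a case.
- **The consequence is limited.** The endpoint is descriptive, with no hypothesis or success threshold, and any error works against the tracer. The shift table already shows the cell in which the missed cases would sit.

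These points limit the size and certainty. They do not remove the gap. Use of 'Other' would vary by physician, no rule recodes its text, and a reader cannot bound the problem from the shift table without knowing which forms were old.

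**Conclusion.** The concern holds as a minor point. SAP 2.6.1 applies one category-pair rule and one denominator to two versions of Questionnaire 2, so the same event can score differently by version. The management-change percentage may be understated, and the new category's percentage has too wide a denominator.

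With 12 to 20 old forms among about 190 participants, the overall percentage cannot be understated by more than 6.3 to 10.5 points. The likely effect is a few points or less, which is a judgement resting on assumed rates of plan-only change. More old forms, or an F-SAF nearer 152, would raise the ceiling in proportion.

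A reader might go further and infer that the headline should be recalculated on amended forms only. The documents do not call for that. Old forms still record moves to surgery, ADT or observation validly, and dropping them would select participants by enrolment date and by how quickly their site gained approval. The co-primary endpoints and the rule for study success are unaffected.

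**What to change.** In SAP 2.6.1:

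1. Derive a flag for the Questionnaire 2 version each participant's physician completed, from the form itself or the site's implementation date.
2. Keep the F-SAF percentage as the headline.
3. Calculate the percentage in the new category only among participants whose form offered it.
4. Add a supportive management-change percentage and shift table restricted to the amended form, or by-version rows in the existing tables.
5. Footnote the pooled results to say that old-form pairs of 'Radiation alone' twice cannot show whether the radiation plan changed.

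The cost is one derived variable, an extra row or table, and slightly smaller denominators in the supportive result. No new data are needed if the form version or implementation dates are on file.

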#### 2.6.2 Statistical hypothesis, model, and method of analysis

For patient-level diagnostic performance parameters:

- Patient-level sensitivity
- Patient-level specificity
- Patient-level negative predictive value
- Patient-level accuracy
- Patient-level correct detection rate
- Patient-level detection rate

The number and percentage of TP, TN, FP, and FN participants will be presented and used to calculate the diagnostic performance parameters.

Two-sided exact binomial 95% CIs for patient-level diagnostic performance parameters will be calculated.

[18F]CTT1057 scan inter-reader variability will be assessed by Fleiss' Kappa statistic (Fleiss 1971) defined below:

$$\kappa_1 = \frac{\bar{P} - \bar{P}_e}{1 - \bar{P}_e}.$$

Let N represent the total number of participants who have evaluable PET/CT, n the number of central readings per participant received (n=3), and k the number of outcome categories (k=2) into which assignments are made. Participants are indexed by i=1,...,N and categories are indexed by j=1,...,k. Let  $n_{ij}$  represent the number of readers who assigned the ith participant to the jth category. Then  $P_i = \frac{1}{n(n-1)} \sum_{j=1}^k n_{ij} (n_{ij}-1)$  and  $\bar{P} = \frac{1}{N} \sum_{i=1}^N P_i$ ;

$$p_{j} = \frac{1}{Nn} \sum_{i=1}^{N} n_{ij}$$
 and  $\bar{P}_{e} = \sum_{j=1}^{k} p_{j}^{2}$ .

A contingency table of N row (N is the number of participants who have evaluable PET/CT) by 2 (the number of outcome categories) will be obtained to summarize the frequency of agreements among the 3 readers for each case and each patient-level outcome (i.e. positive, negative). The counts across each of the N rows will sum up to 3 (number of readers).

Based on the contingency table as described above, a Fleiss's Kappa statistic and corresponding 95% confidence interval will be estimated based on asymptotic estimation of the standard error (i.e.

$$\widehat{se}(\kappa_1) = \frac{\sqrt{2}}{\sum_{j=1}^k p_j (1-p_j) \sqrt{Nn(n-1)}} \sqrt{\left(\sum_{j=1}^k p_j (1-p_j)\right)^2 - \sum_{j=1}^k p_j (1-p_j)(1-2p_j)})$$
(Fleiss,

Nee, Landis 1979; Fleiss J, Levin B, Paik MC 2003) and the normality assumption (i.e. 95% CI can be calculated as:  $\kappa_1 \pm 1.96 \widehat{se}(\kappa_1)$ ). An additional table will be presented to show the

distribution of agreements with the number (%) of scans agreed by two readers and the number (%) of scans agreed by all three readers. Inter-reader variability will be calculated using the F-SAF.

[18F]CTT1057 scan intra-reader variability will be assessed by Cohen's Kappa statistic.

To assess the intra-reader variability, each of the three readers will re-read the same 20 randomly selected cases (with evaluable PET/CT) but each case will be presented to each reader in a random order. The readers will not reference any previous read results nor discuss any of these cases at any time during the read process. Each reader will use the same method to read the randomly presented cases as they did in the previous reads. Intra-reader agreement will first be evaluated separately for each of the 3 readers using Cohen's kappa statistic ( $\kappa_2$ ) as described below:

**Step 1:** A 2 by 2 contingency table (e.g. Table 2-1) will be calculated to summarize the frequency of concordance and discordance for patient-level positivity or negativity. The counts in the table will add up to 20 in total (i.e. a + b + c + d = 20).

Table 2-1 Example 2 by 2 Contingency Table for Each Reader

		New Reads	
		Positive	Negative
Original Reads	Positive	a	ь
	Negative	С	d

**Step 2:** Based on the contingency tables described above, a simple agreement rate, i.e.  $\frac{a+d}{a+b+c+d}$  and its corresponding 95% confidence interval (Agresti A, Coull BA 1998) will be estimated based on normal approximation.

Step 3: Finally, a Cohen's kappa statistic ( $\kappa_2$ ) and its corresponding 95% confidence interval will be estimated (Cohen J 1960; Cohen J 1968; Fleiss J, Levin B, Paik MC 2003) using the formula  $\kappa_2 \pm 1.96SE$ , where  $SE = \sqrt{\frac{p_0(1-p_0)}{N(1-p_e)^2}}$  (McHugh M 2012). Let N denote the number of re-reads (N=20), k the number of categories (k=2),  $n_{i1}$  the number of times the original reads were assigned to i (i=1,...,k) and  $n_{i2}$ the number of times the re-read were assigned to i (i=1,...,k). Then Cohen's kappa can be calculated as  $\kappa = \frac{p_0-p_e}{1-p_e}$ , where  $p_0$  is the relative agreements among the original and re-reads ( $p_0 = \frac{a+d}{a+b+c+d}$  in Table 2-1) and  $p_e = \sum_{i=1}^k \frac{n_{i1}}{N} \frac{n_{i2}}{N}$  ( $p_e = \frac{a+b}{N} \frac{a+c}{N} + \frac{c+d}{N} \frac{b+d}{N}$  in Table 2-1). Intra-reader variability will be calculated for the F-SAF.

For region-level diagnostic performance parameters:

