A central read of the [18F]CTT1057 PET/CT scans will be performed at a CRO by three independent nuclear medicine physicians or radiologists experienced in reading PET, who will be blinded to patient data, including the clinical condition of the patient, results of histopathology/biopsy, results of conventional imaging and PSA levels. Patients and regions will be graded on a two-point scale by each reader (0 = negative; 1 = positive). The 3 PET readers' results will be individually compared to the SoT to generate per-reader performance. An individual PET reader will be considered successful if he/she meets the predefined thresholds for both co-primary endpoints, and at least two of three readers should be successful for overall study positivity.

Regions defined for this study are prostate region (comprising prostate bed/prostate gland and any local invasion of the urinary bladder, rectum or seminal vesicles), PLN region, extra-PLN region, skeletal region and visceral region.

The criteria to be applied for PET positivity is the following:

- A patient will be judged positive if at least one lesion in any region is visually positive.
- A region will be judged as positive if at least one lesion in the region is visually positive.
- Visually PET positive lymph nodes will be considered greater than blood pool (adjacent or mediastinal blood pool)
- PET positive bone lesions will be considered greater than physiologic bone marrow
- PET positive prostate, prostate bed and visceral lesions will be considered greater than physiologic background activity of the involvement organ or anatomic site, as previously described (Eiber et al 2015, Ceci et al 2015, Fendler et al 2019).

Consistency of the PET scan interpretation both between different readers and within readers is an important issue in medical imaging, as it affects portability of results between institutions and may affect patient care. The degree of inter- and intra-reader variability in the qualitative assessment of [18F]CTT1057 PET/CT images will be assessed as a secondary endpoint to ensure consistency of interpretation and hence reliable diagnosis, which has pivotal role in the patient management.

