# 3.1 Primary endpoints(s)

This study is planned to recruit approximately 190 participants. The sample size calculation is based on the co-primary endpoints of region-level CLR and the patient-level PPV of [18F]CTT1057.

The assumptions for sample size calculations are based on the estimates from data available from prior studies.

The primary endpoint is to evaluate region-level CLR (prostate region, PLN, extra-pelvic lymph nodes, skeletal, and visceral) and patient-level PPV of [F]CTT1057 PET for detection of tumor location confirmed by CTS. Based on the results of previous studies, the following distribution of disease across regions are anticipated: Prostate bed: 30%, pelvis: 15%; extrapelvic soft tissue: 20%; bone metastases: 35% (Eiber et al 2015, Ceci et al 2015, Van Leeuwen et al 2016). It is anticipated that the CLR for the five regions and for all regions combined using conventional imaging ranges from 30-60%. An overall CLR for [F]CTT1057 PET of at most 50% will be considered as unacceptably low. Hence, the null hypothesis that the CLR is at most 50% will be tested against the alternative hypothesis that the CLR is greater than 50%.

The BCR population targeted in this study is expected to have similar PSA values as prior studies (Morris et al 2020) of approved diagnostic PET agents for PCa such as [F]-fluciclovine, which had a 27% PPV for patients with PSA values that were less than 1.78, as noted in their summary basis of approval. Thus, a patient-level PPV of 20% will be considered as unacceptably low. The [F]CTT1057 positive patient rate (detection rate) for the study population is 80% based on [F]-fluciclovine studies. The sample size calculation will be performed based on the null and alternative hypotheses as follows.

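### The SAP's standard error for Fleiss' kappa is always 1/sqrt(3N), the value for kappa = 0, so the planned 95% CI for inter-reader agreement is not valid in general

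*SAP*

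**What the plan says.** Inter-reader agreement on the [18F]CTT1057 scan is a secondary endpoint. Protocol 4.1 says reader variability is assessed "to ensure consistency of interpretation and hence reliable diagnosis".

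SAP 2.6.2 defines Fleiss' kappa with "n the number of central readings per participant received (n=3), and k the number of outcome categories (k=2", the categories being "each patient-level outcome (i.e. positive, negative". It prints one closed-form SE that depends only on the category proportions p_j, the number of participants N and the number of readers n. It then says that a "95% confidence interval will be estimated based on asymptotic estimation of the standard error" and "the normality assumption (i.e. 95% CI can be calculated as" kappa ± 1.96 SE. No other variance for Fleiss' kappa is given, and no test of kappa = 0 is planned. On the analysis set: "Inter-reader variability will be calculated using the F-SAF", limited to participants with evaluable PET/CT.

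The same section also plans a table showing the "distribution of agreements with the number (%) of scans agreed by two readers and the number (%) of scans agreed by all three readers". The Cohen's kappa SE used there for intra-reader agreement does depend on the observed agreement.

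**The concern.** The width of an interval for kappa should depend on how well the readers agreed. The printed Fleiss SE contains no term for observed agreement, which suggests a variance derived under the hypothesis of no agreement. Such a variance can test kappa = 0, but it does not in general describe the sampling error around a kappa of, say, 0.6 or 0.9.

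At moderate agreement, where readers of the report most need to know how uncertain the estimate is, the interval would look too precise. At high agreement it would be too wide and could run above 1, which kappa cannot exceed. Agreement also bears on how to read the rule in SAP 2.5.2 that two of three readers must succeed.

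**Working it through.** **Inputs**
- n = 3 readers, k = 2 categories, SE formula and CI form: SAP 2.6.2.
- N: the set for this endpoint is F-SAF participants with evaluable PET/CT. The documents give no count for it. The planned minimum of 152 evaluable for the co-primary endpoints and the 190 enrolled (SAP 3) are used as illustrations.
- Positive rate: SAP 3.1 says the "positive patient rate (detection rate) for the study population is 80"%. Rates of 50% and 90% are assumptions outside the plan.
- True kappa: not stated, so a range is used.

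**Algebra.** Write p_1 = p, p_2 = q = 1 − p and S = Σ p_j(1 − p_j). The printed formula is

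`SE = sqrt(2) / (S · sqrt(N n (n−1))) · sqrt( S² − Σ p_j(1−p_j)(1−2p_j) )`

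- S = pq + qp = 2pq.
- Subtracted sum: pq(1 − 2p) + qp(1 − 2q) = pq(q − p) + pq(p − q) = 0.
- Hence SE = sqrt(2)/(S·sqrt(6N)) · S = sqrt(2/(6N)) = **1/sqrt(3N)** for every 0 < p < 1. If every read falls in one category, the formula is 0/0.

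**Numbers**
- N = 152: SE = 1/sqrt(456) = 0.0468; half-width 1.96 × 0.0468 = 0.092.
- N = 190: SE = 1/sqrt(570) = 0.0419; half-width 0.082.
- Evaluating the printed formula at p = 0.05, 0.2, 0.5, 0.8 and 0.95 gives the same SE to six decimals.
- Perfect agreement at N = 152: 1 ± 0.092, that is 0.908 to 1.092.

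**Comparison with the true sampling error.** Three exchangeable readers were simulated under two models of how their reads correlate: a beta-binomial with intraclass correlation equal to kappa, and a mixture in which all readers agree with probability kappa and otherwise read independently. There were 100,000 trials per cell. Results for N = 152 and 80% positive (planned SE 0.0468):

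| True kappa | True SD, beta-binomial / mixture | True SD ÷ planned SE | Coverage of planned 95% CI | Upper limit above 1 |
|---|---|---|---|---|
| 0 | 0.0469 / 0.0465 | 1.00 / 0.99 | 95.2% / 95.4% | 0% |
| 0.2 | 0.0619 / 0.0700 | 1.32 / 1.50 | 86.2% / 80.8% | 0% |
| 0.4 | 0.0674 / 0.0750 | 1.44 / 1.60 | 82.5% / 77.9% | 0% |
| 0.6 | 0.0640 / 0.0691 | 1.37 / 1.48 | 85.0% / 82.1% | 0% |
| 0.8 | 0.0503 / 0.0523 | 1.08 / 1.12 | 93.3% / 92.2% | about 1% |
| 0.9 | 0.0368 / 0.0377 | 0.79 / 0.80 | 98.6% / 98.3% | about 42% |

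The match at kappa = 0 confirms which SE this is. A finer beta-binomial grid (40,000 trials per cell) gives coverage of 88% at kappa 0.7, 91% at 0.75, 96% at 0.85 and over 99% at 0.95, where the upper limit passes 1 in 93% of trials.

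At N = 190 coverage changes by no more than about one point, but the share of upper limits above 1 at kappa 0.9 falls to about 29%.

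For kappa 0.4 to 0.6 at N = 152, coverage is 91–93% at 50% positive. At 90% positive it is 69–71% under the beta-binomial and 61–66% under the mixture.

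**The case against.** The strongest counter-argument is about weight. Inter-reader kappa is descriptive: no hypothesis, threshold or decision rule uses it, and study success rests on each reader meeting the CLR and PPV criteria. The agreement table shows reader consistency without this interval. Near kappa 0.8 at 80% positive the planned interval is about right. All of this stands and limits the consequence, but the interval as written is still wrong for most values of kappa, and it is close near 0.8 only because the two SEs happen to cross there.

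The coverage figures depend on the reader-correlation model and on N. That also stands, which is why two models and two values of N are shown. The second model makes the under-coverage worse.

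Finally, the jackknife with Fisher z is one choice among several, and its coverage is partly conditional, because perfect-agreement trials, where it is undefined, are excluded. The excluded share is small at 80% positive and N = 152 (0.1% at kappa 0.9, 2.5% at 0.95), but about 13% at 90% positive and kappa 0.95. In the RP and RT subgroups, whose sizes are not given, the exclusion would matter more. With an assumed N = 50 and 80% positive, perfect agreement occurs in about 9% of trials at kappa 0.9 and 30% at 0.95. At 90% positive and kappa 0.4 the z interval would cover about 86–88%, against 62–68% for the planned one. The proposal is therefore better there, but not fully accurate.

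**Conclusion.** The concern holds. That the SE is fixed at 1/sqrt(3N), and is the value for kappa = 0, is exact and needs no assumption beyond the SAP's own three readers and two categories. The size of the coverage error rests on assumed kappa values, exchangeable readers, the two correlation models and N between 152 and 190.

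At the planned positive rate the interval is too narrow below a kappa of about 0.75 and too wide from about 0.9 upward. This should be corrected because it misstates the precision of a named secondary endpoint. It does not alter the kappa point estimate, the agreement table or any co-primary conclusion.

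**What to change.** In SAP 2.6.2, replace the Fleiss SE and interval as follows:

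- Compute a participant-level jackknife SE of kappa, leaving out one participant with all three reads each time.
- Form the interval on the Fisher z scale: z = atanh(kappa), SE_z = SE_jack/(1 − kappa²), limits z ± 1.96 SE_z, back-transformed with tanh. The limits cannot pass 1.
- If all three readers agree on every scan, the jackknife SE is 0 and z is undefined. Report kappa = 1 without this interval, together with the exact binomial CI for the proportion of scans on which all three agree. For 152/152 the lower limit is 0.025^(1/152) = 0.976.
- Keep the printed formula only for a test of kappa = 0, if one is wanted.

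At 80% positive and N = 152 (beta-binomial, perfect-agreement trials excluded), the z interval covers 94.7%, 94.9%, 95.5%, 96.2% and 96.5% at kappa 0.4, 0.6, 0.8, 0.9 and 0.95. At kappa 0.95 the untransformed jackknife falls to 88.6% and a percentile bootstrap to 91%, which is the reason for the z scale. Another variance that is valid at non-zero kappa would also remove the defect.

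The cost is two SAP sentences and a few lines of code, with no new data. At 80% positive and N = 152, the mean interval width goes from a constant 0.184 to 0.265 at kappa 0.4, 0.253 at 0.6 and 0.154 at 0.9.
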